7.1.4 Serious Adverse Events

An SAE or reaction is any untoward medical occurrence that at any dose:

- Results in death
- Is life-threatening
- Requires inpatient hospitalization or prolongation of existing hospitalization, with the exception of:
 - Visits to the emergency room or hospital department that do not result in an overnight hospital admission
 - Elective surgery for a pre-existing condition that has not worsened
 - Routine health assessments requiring admission not associated with any deterioration in condition
 - Social admission (lack of housing, family circumstances, etc.)
- Results in persistent or significant disability or incapacity
- Is a congenital anomaly or birth defect
- Is an important medical event (eg, intensive treatment in an emergency room or at home for allergic bronchospasm, blood dyscrasias or convulsions that do not result in hospitalization, development of drug dependency or drug abuse, or malignancy tumors [histologically different from the primary tumor])

Note: The term “life-threatening” in the definition of “serious” refers to an event in which the subject was at risk of death at the time of the event; it does not refer to an event that hypothetically might have caused death if it were more severe.

Medical and scientific judgment should be exercised in deciding whether expedited reporting is appropriate in other situations, such as important medical events that may not be immediately life-threatening or result in death or hospitalization, but may jeopardize the subject or may require intervention to prevent one of the other outcomes listed in the definition above. These should also usually be considered serious.

Seriousness (not severity) serves as a guide for defining regulatory reporting obligations. An SAE is not necessarily severe, eg, a hospitalization for a diagnostic procedure must be reported as an SAE even though the occurrence is not medically serious. By the same token, a severe AE is not necessarily serious: nausea of several hours' duration may be rated as severe but may not be considered serious.

7.1.5 Unexpected Adverse Drug Reactions

An unexpected adverse drug reaction (ADR) is a reaction for which the nature or severity is not consistent with the applicable product information (see current Investigator's Brochure). Until product information is amended, expedited reporting is required for additional occurrences of the reaction. Reports that add significant information on specificity or severity of a known, already documented SAE constitute unexpected events. For example, an event more specific or more severe than described in the Investigator's Brochure would be considered "unexpected." Specific examples would be (a) acute renal failure as a labeled ADR with a subsequent new report of interstitial nephritis and (b) hepatitis with a first report of fulminant hepatitis.

Assessing Intensity and Relationship

All AEs will be assessed on 2 descriptive parameters: intensity and relationship to the study drug:

1. Intensity refers to the severity of an event and references the impact on a subject's functioning.
2. Relationship refers to the likelihood that the event being assessed was caused by the study drug.

Intensity

Each AE will be classified according to the following criteria:

Mild:	The AE does not interfere in a significant manner with the subject's normal level of functioning.
Moderate:	The AE produces some impairment of functioning but is not hazardous to the subject's health.
Severe:	The AE produces significant impairment of functioning or incapacitation and is a definite hazard to the subject's health.

When changes in the intensity of an AE occur more frequently than once a day, the maximum intensity for the experience should be noted. If the intensity category changes over a number of days, those changes should be recorded separately (with distinct onset dates).

Relationship

Each AE will be assessed as to its relationship to the study drug based on the following criteria. Although the attribution by the investigator will be collected for reported events, for analytic purposes a temporal association with the use of the study drug will be assumed sufficient for at least plausible association.

Not related:	No causal relationship exists between the study drug and the AE, but an obvious alternative cause exists, eg, the subject's underlying medical condition or concomitant therapy.
Related:	There is a reasonable/plausible possibility that the AE may have been caused by the study drug.

When assessing the relationship to the study drug, the following criteria will be considered:

- Temporal relationship
- Positive rechallenge
- Positive dechallenge (resolution upon stopping the study drug, in absence of other intervention or treatment)
- Known class effect
- Biological plausibility
- Lack of alternative explanation—concomitant drug or disease

7.1.6 Reporting Procedures and Requirements

Adverse Events

AE recording will begin after the first dose of study drug is administered the morning after baseline. Thereafter, AEs will be ascertained by asking the subject how he/she has been since the last visit. Any AEs occurring before the start of treatment (ie, before the first dose of the study drug) will be recorded in the medical history only. If the investigator detects an AE in a study subject within 1 month (4 weeks, -/+ 1 week) of the last scheduled follow-up visit this will also be collected. All AEs will be followed until resolved or stable and the outcome documented on the CRF.

Also, the sign, symptom, or disease present before starting the treatment period are only considered AEs if they worsen after starting the treatment period.

The investigator should report all information about AEs on the AE/SAE section of the Case Report Form (CRF). Whenever possible, an AE will be reported using a diagnostic term (eg, “common cold” or “upper respiratory infection” rather than “runny nose, cough, mild fever”) and should be described with the attributes.

Serious Adverse Events

Each AE will be assessed to determine whether it meets seriousness criteria (Section 7.1.2.2). If the AE is considered serious, the investigator should report this event to Agene Biotech as outlined below and to the Institutional Review Board (IRB) & Data Safety Monitoring Board (DSMB) according to their standard operating procedures.

All information about SAEs will be collected and reported by entering the SAE information in the AE CRF. The investigator should send the initial report to the Site PI and to Agene Biotech within 24 hours of becoming aware of the SAE and followed by follow-up reports as soon as possible, whether the events are deemed related to the study drug or not. The information provided in the AE system should be as complete as possible, but minimally it must contain the following:

- Subject number
- Brief description of the SAE (diagnosis or signs/symptoms)
- Serious criteria
- Causality assessment
- Assessment of the intensity of the event

Agene Biotech will receive notification of the initial SAE via an e-mail from MCW Study Team. Site personnel will complete the paper SAE report form, scan and e-mail it within 24 hours to the following address: [contact]

SAEs that are ongoing should be followed until resolved or stabilized to a level acceptable to the investigator. Information not available at the time of the initial report (eg, an end date for the AE, laboratory values received after the report, or hospital discharge summary) must be documented on a follow-up form. All follow-up information must be reported in the same timelines as initial information.

Any SAEs considered related to the study drug and discovered by the study team at any interval after the study must also be reported to the Agene Biotech within 24 hours following knowledge of the event.

Sponsor Reporting of Suspected Unexpected Adverse Reactions to Regulatory Authorities (SUSAR)

Per 21 CFR 312.32[c](1)(i)) the Sponsor (MCW) must report in an **IND Safety Report** any suspected adverse reaction to study treatment that is both serious and unexpected. Before submitting an IND safety report, the Sponsor needs to ensure that the event meets all three of the definitions:

- Suspected adverse reaction
- Serious
- Unexpected

The Sponsor/MCW Study Team will submit a **FDA Form 3500A MedWatch** for expedited reporting of all events that qualify for expedited reporting. Refer to the Form FDA 3500A Supplemental Manual for instructions and timelines on mandatory reporting.

Unblinding Treatment Allocation

Generally, only SUSARs for which the treatment allocation of the subject is unblinded should be reported by the sponsor to the pertinent regulatory authorities.

When an event may be a SUSAR, the blind should be broken only for that specific subject, and only if knowledge of the study drug assignment is material to the medical management of the AE. When unblinded to assist in the medical management, the blind for that subject should be maintained for individuals responsible for the ongoing conduct of the study (eg, management, monitors, and investigators) and those responsible for data analysis and interpretation of results at the conclusion of the study (eg, biometrics personnel).

Unblinded information should only be accessible to those who need to be involved in the safety reporting to pertinent regulatory authorities, independent ethics committees/independent review boards (IRBs) and DSMBs, or individuals performing ongoing safety evaluations during the study.

Reporting to Institutional Review Board and Data Safety Monitoring Board

The IRB/DSMB will be notified of any SUSARs according to local regulations and within the designated timeframe. Refer to MCW IRB Reporting Policy. These will be reported to the DSMB in parallel.

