Visit 1 (baseline) and Visits 2 and 4 (which are separated by a 4-week washout period, -/+ 1 week) include a physical and neurological examination, a neuropsychological assessment, and fMRI scans. At baseline visit and the third visit, each subject will be provided with the study medication. At the end of the period 1, period 2 and washout period, each participant will have a blood draw. Treatment compliance will be assessed by reviewing participant self-reports at the end of each period, bottle return and pill count, and analyzing of AGB101 levetiracetam blood values at each study visit. The study team is blind to the APOE status of the participants and AGB101 levetiracetam blood levels until the final group analysis of the data. The company Agenebio, Inc. will provide AGB101 levetiracetam extended release tablets as well as placebo. The Froedtert Hospital Investigational Drug Service will randomize participants to the treatment conditions, dispense the study medication, and control blinding and unblinding of study data according to standard clinical trial procedures. Data safety is monitored by three data safety monitoring board (DSMB) members who are not related to the study, in collaboration with the Froedtert Hospital Investigational Drug Service.

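### Protocol Section 7.1.6 makes the report of every serious unexpected suspected reaction mandatory, but by default its unblinding rules keep from the regulator those whose management does not depend on the assignment

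*Protocol*

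**What the plan says.** Three rules stand under two adjacent headings of Protocol Section 7.1.6.

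- **Duty.** Under the heading on sponsor reporting to regulatory authorities, the sponsor must send an IND safety report for "any suspected adverse reaction to study treatment that is both serious and unexpected". The check before submission is that "the Sponsor needs to ensure that the event meets all three of the definitions": suspected adverse reaction, serious, unexpected. A MedWatch form is then filed "for expedited reporting of all events that qualify for expedited reporting". The filer is named as the sponsor together with the study team.
- **Filter.** Under the heading on unblinding: "Generally, only SUSARs for which the treatment allocation of the subject is unblinded should be reported by the sponsor to the pertinent regulatory authorities".
- **Gate.** Under the same heading, when an event may be a SUSAR, the blind is broken for that subject alone and "only if knowledge of the study drug assignment is material to the medical management of the AE".

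Four other statements bear on the point.

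- On access, Section 7.1.6 adds: "Unblinded information should only be accessible to those who need to be involved in the safety reporting to pertinent regulatory authorities", and it extends that access to ethics bodies, the DSMB and those doing ongoing safety evaluation.
- On the other recipients, it says: "The IRB/DSMB will be notified of any SUSARs according to local regulations and within the designated timeframe".
- Section 4.1 has the Investigational Drug Service "control blinding and unblinding of study data according to standard clinical trial procedures".
- Section 5.4.7 keeps both participants and the study team blind to treatment.

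**The concern.** The duty has no unblinding condition. The filter adds one, and the gate then closes the only written way to meet it for some events. Staff who follow the unblinding paragraph for such an event would, by default, not send a report that the preceding paragraph makes mandatory. Staff who send it blinded would depart from the filter, and staff who break the blind in order to send it would breach the gate.

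At stake is whether the regulator hears promptly of a serious, unexpected and possibly drug-related event in cognitively normal volunteers. The point does not touch sample size, error rates or the planned analyses.

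**Working it through.** No arithmetic applies. The check is whether one event can satisfy all three rules.

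**Step 1: state the rules.**

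- Duty: suspected, serious and unexpected → must be reported.
- Filter: reported to the authorities, generally, only if the subject's allocation is unblinded.
- Gate: unblinded only if the assignment matters to managing the event.

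**Step 2: split the qualifying events by whether management depends on the assignment.**

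| Management depends on the assignment? | Duty | Gate | Filter | All three met? |
|---|---|---|---|---|
| Yes | report | blind may be broken | report allowed | yes |
| No | report | blind stays | by default, no report | no |

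The second row is not empty. It covers a reaction that is fatal, one that has already resolved, and one treated the same way on drug or placebo. It may also cover related events found after the study, a case Section 7.1.6 foresees when it requires them to go to the drug supplier. Dosing has then ended, and the assignment may no longer affect care.

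**Step 3: find which rules produce the conflict.**

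- Without the filter, the event could be reported blinded.
- Without the gate, the blind could be broken and the event reported.
- Without the duty, nothing would require the report.

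So any two of the rules can stand together, and the conflict needs all three. Changing the filter or the gate can remove it.

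**Step 4: look for an exception elsewhere.**

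- Section 7.1.5 calls for expedited reporting of repeat unexpected reactions. It sets no unblinding condition and gives no ground for unblinding.
- Section 4.1 gives the Investigational Drug Service control of unblinding but refers only to standard procedures. It describes no route for a regulatory report.
- Section 5.4.7, in the protocol and as repeated in the SAP, covers blinding only. The rest of the available SAP text does not address the point.
- The access sentence limits who may see a code already broken. It gives no reason to break one.

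None of these removes the conflict.

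**Step 5: check the other recipients.** The serious adverse event procedure in Section 7.1.6 sends the initial report to the drug supplier within 24 hours, whether or not the event is judged related. It also sends serious events to the IRB and DSMB under their own procedures. The IRB and DSMB are separately told of any SUSAR. None of these routes depends on unblinding, so the conflict is confined to the report to regulatory authorities.

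**The case against.** The strongest reply is that the text is loosely drafted but not a bar. The filter opens with a word that makes it a default and uses the weaker verb of recommendation, while the duty is stated as an obligation and tied to a regulation. A careful reader could let the obligation prevail. The access sentence assumes that people who report to authorities may hold unblinded information. The sentence on keeping others blind after unblinding for medical reasons can also be read to imply other occasions for unblinding.

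Part of this stands. The filter withholds the report by default, not absolutely, and unblinding for reporting seems to have been contemplated. But the section gives no criteria for departing from the default, and the gate's condition is worded as exclusive. What was contemplated was not written down, and the staff member facing the event has two instructions that differ.

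A reader might also infer that the IRB and DSMB could miss such an event. The documents do not support that: both are notified without any unblinding condition. Those routes reduce the practical harm but do not discharge the sponsor's separate duty to the regulator.

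Finally, it might be argued that allowing unblinding for reports would damage the trial blind. That objection has some force, because the named filer includes the study team, which Section 5.4.7 keeps blind. It bears on how the correction is made, not on whether one is needed.

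**Conclusion.** The concern holds in a limited form. For a serious, unexpected, suspected reaction whose management does not depend on the assignment, the three rules of Section 7.1.6 cannot all be followed, and the default outcome is that the regulator is not told.

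The number of such events cannot be estimated from the documents. It may be small, with 50 subjects planned and two treatment periods nominally of 2 weeks each. The conclusion rests on reading the gate's condition as exclusive, as it is worded, and on there being no reporting route beyond the text available.

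A reader might infer that the plan forbids these reports outright. It does not, because the restriction is stated as a general rule. This is an internal inconsistency in safety reporting that should be corrected.

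**What to change.** Reconcile the two parts of Section 7.1.6.

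1. Amend the filter so that it does not limit the mandatory report. For example: *The sponsor's expedited report of an event that meets all three definitions does not depend on whether the subject's allocation has been unblinded.*
2. State explicitly whether the blind may be broken for one subject when an event meets all three definitions, in addition to the existing medical ground.
3. If it may, say who receives the allocation. The Investigational Drug Service already controls unblinding and can supply it for the report to a named role outside the blinded study team, so that investigators and analysts stay blind.

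Adding a ground for unblinding while leaving the filter as it stands would not be enough, because the filter would still make the report conditional on unblinding.

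The cost is a sentence or two and one practical change: where allocation is supplied, the filing step must be routed around the blinded team, because the section now names the study team as joint filer. This matters more than in a parallel-group trial. Each subject receives both treatments, so unblinding one period reveals the other. Each subject unblinded is 1/50 = 2% of the planned sample, or 1/25 = 4% of a genotype group. With the allocation held outside the team, the analysis blind is kept.

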7.2. MRI Safety

The MRI scanner device is a U.S. Food and Drug Administration (FDA)-cleared device for safe and noninvasive imaging of the interior of the human body. The GE MR750 MRI uses a 32-channel receive-only head coil, which is an investigational device. See below for further information on the 32-channel receive-only head coil. The pulse sequences employed in this study were developed based on multiecho sequence by GE Healthcare, which constrains the pulse sequences to operate within the FDA limits for safe operation with respect to gradient switching (dB/dt) and RF power (specific absorption rate [SAR]). The proposed MRI scans are NOT for a use of substantial importance in diagnosing, curing, mitigating, or treating disease or otherwise preventing impairment of human health, and they do not present a potential for serious risk to the health, safety, or welfare of a subject. The scanner also restricts the software from exceeding FDA safety levels. The scanner monitors the SAR for research scans just as it does for all other scans. Thus, the scanner with the software fully engaged operates, from a technical design and functional standpoint, as a **nonsignificant risk** device in accordance with 21 CFR 812. By staying below these limits, the operating conditions of the MRI device are generally deemed, in and of themselves, to make the MRI device a nonsignificant risk device.

The Nova Medical 32-channel head coil (model number NMSC075-32-3GE-MR750) is an investigational device that is not approved by FDA for clinical use. This coil device includes multiple features for safe operation involving human studies. The 32-channel coil is designed and constructed as a receive-only detector of RF signals that are emitted by the brain following the RF excitation generated by the GE Healthcare MRI scanner, which is FDA approved. During the RF excitation by the scanner, the coil device is decoupled (made inactive) through redundant circuitry; thus, the coil device never transmits RF to the subject and, therefore, it has no impact on subject risk or safety.

More specifically, the coil design and construction include the following safety features: **1)** High-voltage breakdown (>2 kV) UL-94V0 flame retardant housing. **2)** Rugged construction to ensure safe operation in case of rough handling. **3)** Active detuning circuitry providing greater than 35 db isolation per element. **4)** High power passive detuning circuits in case primary detuning circuitry fails. **5)** Multiple common mode traps in all receive coil cables. **6)** Minimum of 5 mm spacing between coil conductors and patient contact.

Additionally, the coil was designed and manufactured under an ISO 13485 certified quality management system. As part of this quality system, Nova Medical has conducted a failure means and effects analysis

(FEMA) of this product, and we feel that it is a nonsignificant risk under foreseeable normal conditions when used on the 3T GE X750 MRI scanners at MCW.

The Medical College of Wisconsin has installed a new GE 3T MRI scanner (Signa Premier) equipped with a 48-channel receive-only head coil, which is FDA-approved. We will use the new GE 3T Signa Premier MRI scanner and 48-channel head coil for study subjects. The GE750 MRI scanner with the 32-channel head coil will be used as a back-up for scheduling purposes.

7.3. MRI Safety Screening

MCW-specific magnetic resonance (MR) safety screening procedures will be followed. All participants will be screened for medical devices, implants, and metal prior to undergoing MRI, first at the screening visit (Visit -1) and again prior to entering the scanner room on Visits 1, 2 and 4. If it is necessary to review medical records to confirm contraindication, a review of medical records (e.g., previous surgeries) will take place prior to the scheduled visit. During the screening process, participants will also be questioned about their ability to temporarily remove transdermal patches (such as birth control or nicotine patches). Women of child-bearing potential will be asked to confirm that they are not pregnant when signing the ICF. If a woman has concerns or is uncertain of her pregnancy status, she will be excluded, as the risks of an MRI scan to pregnant women are currently unknown. The risks related to an MRI are minimal for a properly administered visit. The MR technicians are trained and prepared to deal with any problems that may arise.

